9.2.1 Selection of study population

Site selection:

Sites with access to paper/electronic medical charts/electronic health record (EHR) that have treated patients according to inclusion criteria:

1. Adult patients
2. diagnosed with Epidermal Growth Factor Receptor Tyrosine Kinase Inhibitor (EGFR-TKI) naïve advanced EGFR mutated non-small cell lung cancer (NSCLC),
3. treated for Epidermal Growth Factor Receptor (EGFR) mutated NSCLC within regular clinical practice.
4. Informed and privacy consent signature must be obtained depending on local regulations.

More specific inclusion criteria for each cohort are the following:

Uncommon mutation cohort:

5. Patients harbouring uncommon or compound EGFR mutations
6. Patients who started with either afatinib (Gi(I)otrif[®]), gefitinib (Iressa), erlotinib (Tarceva), or osimertinib (Tagrisso) in the first- or second-line setting within regular clinical practice
7. Patients must have started EGFR-TKI treatment at least 12 months prior to data entry.

Sequencing cohort:

5. Patients with common EGFR mutations (Del19, L858R)
6. Patients were treated with afatinib (Gi(I)otrif[®]) in the first-line setting and for acquired T790M mutation with osimertinib in the second line;
7. Patients must have started osimertinib treatment at least 10 months prior to data entry. Patients treated with osimertinib within an early access program/ compassionate use program (EAP/CUP) are allowed

Main exclusion criteria:

1. Patients treated for EGFR mutated NSCLC within a clinical trial or participated in GioTag study.
2. Patients with active brain metastases at start of EGFR-TKI therapy (independent of treatment line)
3. For uncommon mutation cohort: Patients treated with osimertinib with no further uncommon mutation than acquired T790M

Deceased patients fulfilling the eligibility criteria should be enrolled whenever possible.

Uncommon mutation cohort: Patients treated with EGFR-TKI in interventional trials are excluded to ensure the non-interventional setting of this study. The threshold of start of treatment at least 12 months respectively prior to data entry was chosen based on the median PFS reported for patients being treated with afatinib in the LUX-Lung 2, -3, -and 6 trials ([P15-05932](#)) to avoid early censoring and enable collection of mature data on adverse drug

reactions (ADRs) and treatment duration. All patients fulfilling inclusion and exclusion criteria from a site will be entered to avoid bias.

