- “4. Informed and privacy consent signature obtained depending on local regulations” in the ELIGIBILITY CRITERIA form [**EC. EC_IC_4**] = “Yes” OR “Not applicable: ICF waiver/Opt-out/No opposition applies”, AND
- “4. Informed and privacy consent signature obtained depending on local regulations” in the PROTOCOL DEVIATION FORM [**PDF. PDF_IC4**] is not flagged AND
- “Date of data collection (dd/mmm/yyyy)” [**PI. PI_date_coll**] is not missing.

Moreover, for patients with “4. Informed and privacy consent signature obtained depending on local regulations” in the ELIGIBILITY CRITERIA form [**EC. EC_IC_4**] = “Yes, it will be also verified that:

- “Date of informed consent form signature by the patient or by next of kin* (dd/mmm/yyyy)” [**PI. PI_date_IC**] <= “Date of data collection (dd/mmm/yyyy)” [**PI. PI_date_coll**] AND
- “Date of privacy form signature by the patient or by next of kin* (dd/mmm/yyyy)” [**PI. PI_date_priv**] <= “Date of data collection (dd/mmm/yyyy)” [**PI. PI_date_coll**]

During data elaboration this criterion will be critically reviewed and discussed, depending also on specificities of sites and countries local regulations.

Criterion 5 (UNCOMMON MUTATION COHORT). Patient harbouring uncommon or compound EGFR mutations

- “Cohort” [**PI. PI_coh_ty**] = “Uncommon Mutation cohort” AND
- “5. Patient harbouring uncommon or compound EGFR mutations” in the ELIGIBILITY CRITERIA form [**EC. EC_IC_5umc**] = “Yes” AND
- “5. Patient harbouring uncommon or compound EGFR mutations” in the PROTOCOL DEVIATION FORM [**PDF. PDF_IC5_umc**] is not flagged AND
- At least one uncommon mutation shall be present on the start date of the Index EGFR-TKI therapy (as defined in “Chapter 3”), according to the fields:
 - “EGFR mutations at start of first-line treatment” [**First-line treatment period / MUT1. MUT1_unc**]
OR
 - “EGFR mutations at start of second-line treatment” in the MUTATIONS form of the [**Second-line treatment period / MUT2. MUT2_mut_start**]

Criterion 5 (SEQUENCING COHORT). Patient with common EGFR mutations (Del19, L858R)

- “Cohort” [**PI. PI_coh_ty**] = “Sequencing cohort” AND
- “5. Patient with common EGFR mutations (Del19, L858R)” in the ELIGIBILITY CRITERIA form [**EC. EC_IC_5sc**] = “Yes” AND
- “5. Patient with common EGFR mutations (Del19, L858R)” in the PROTOCOL DEVIATION FORM [**PDF. PDF_IC5_sc**] is not flagged AND

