- “EGFR mutations at start of second-line treatment” [Second-line treatment period / MUT2. MUT2_mut_start] includes “T790M”

Criterion 7 (UNCOMMON MUTATION COHORT). Patient has started EGFR-TKI treatment at least 12 months prior to data entry

- “Cohort” [PI. PI_coh_ty] = “Uncommon Mutation cohort” AND
- “7. Patient has started EGFR-TKI treatment at least 12 months prior to data entry” in the ELIGIBILITY CRITERIA form [EC. EC_IC_7umc] = “Yes” AND
- “7. Patient has started EGFR-TKI treatment at least 12 months prior to data entry” in the PROTOCOL DEVIATION FORM [PDF. PDF_IC7_umc] is not flagged AND
- Start date of the Index EGFR-TKI therapy (as defined in “Chapter 3”) is lower than or equal to (“Date of data collection (dd/mmm/yyyy)” [PI. PI_date_coll] – 11.50 months) (*)

This line shall start in presence of at least one uncommon/compound mutation (as described in the definition of the calculated variable “Index EGFR-TKI therapy”: see “Chapter 3”).

(*) this means that if the start date of the index EGFR-TKI therapy is 11.49 months before date of data collection, the patient violates this criterion. This tolerance window has been agreed with the Sponsor during the Data Analysis Strategic Meeting, and will not be further discussed. Only in case exact day is not known and this makes the evaluation critical with the respect to the tolerance window, then case-by-case discussion will be done with the Sponsor.

In case the Index therapy line is an EGFR-TKI given in combination with chemotherapy, a query will be raised in order to ensure that the treatment line was administered according to regular clinical practice.

Criterion 7 (SEQUENCING COHORT). Patient has started osimertinib treatment at least 10 months prior to data entry

- “Cohort” [PI. PI_coh_ty] = “Sequencing cohort” AND
- “7. Patient has started osimertinib treatment at least 10 months prior to data entry” in the ELIGIBILITY CRITERIA form [EC. EC_IC_7sc] = “Yes” AND
- “7. Patient has started osimertinib treatment at least 10 months prior to data entry” in the PROTOCOL DEVIATION FORM [PDF. PDF_IC7_sc] is not flagged AND
- Start date of the Index EGFR-TKI therapy (as defined in “Chapter 3”) is lower than or equal to (“Date of data collection (dd/mmm/yyyy)” [PI. PI_date_coll] – 9.50 months) (*)

This line shall start in presence of at least one common mutation (as described in the definition of the calculated variable “Index EGFR-TKI therapy”: see “Chapter 3”).

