- “3. Patient treated with osimertinib with no further uncommon mutation than acquired T790M” in the PROTOCOL DEVIATION FORM [[PDF. PDF_EC3_umc](#)] is not flagged AND
- If the first-line (as defined in “Chapter 3”) is “Osimertinib”, then the following condition shall NOT be verified: no options selected (excluding “Del19” and “L858R”) in field “EGFR mutations at start of first-line treatment” [[First-line treatment period / MUT1. MUT1_unc](#)] AND only option “T790M” is selected in field “EGFR mutations at start of second-line treatment” [[Second-line treatment period / MUT2. MUT2_mut_start](#)]
- If the second-line (as defined in “Chapter 3”) is “Osimertinib”, then the following condition shall NOT be verified: no options selected (excluding “Del19” and “L858R”) in field “EGFR mutations at start of first-line treatment” [[First-line treatment period / MUT1. MUT1_unc](#)] AND no options selected (excluding “Del19” and “L858R”) in field “EGFR mutations at start of second-line treatment” [[Second-line treatment period / MUT2. MUT2_mut_start](#)] AND only option “T790M” is selected in field “EGFR mutations” at stop of second-line treatment/within end of observation [[Second-line treatment period / MUT2. MUT2_mut_stop](#)]

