- from the OSIMERTINIB ADMINISTRATION DETAILS form (only for the SEQUENCING COHORT), from the field [OAD. OAD_dose] of the record with earliest non-missing start date (recorded in field [OAD. OAD_start_date]);
- from the EGFR-TKI ADMINISTRATION DETAILS form (only for the UNCOMMON MUTATION COHORT), from the field [EAD. EAD_dose] of the record with earliest non-missing start date (recorded field [EAD. EAD_start_date]). The same patient could have one or two lines of EGFR-TKI recorded in this form, and each line is identified by the field "Type of EGFR-TKI" [EAD. EAD_EGFR]: therefore, for each line recorded in this form, it will be possible to identify the starting dose with the rule defined above.

Index EGFR-TKI therapy

- *Uncommon mutation cohort*: it will correspond to the therapy recorded in the NSCLC TREATMENT form, either at [First-line treatment period] or [Second-line treatment period] depending on the following conditions:
 - [First-line treatment period] is the time point to consider if:
 - “Type of treatment” [First-line treatment period / TREAT. TREAT_ty] = “EGFR-TKI” AND
 - “Start date of this line (dd/mmm/yyyy)” [First-line treatment period / TREAT. TREAT_start_date] is lower than or equal to (“Date of data collection (dd/mmm/yyyy)” [PI. PI_date_coll] – 11.50 months) AND
 - “EGFR mutations at start of first-line treatment” [First-line treatment period / MUT1. MUT1_unc] has at least one of the options selected (excluding “Del19” and “L858R”) (*)
 - Otherwise, if the above-specified condition is not met, then the [Second-line treatment period] is the time point to consider if:
 - “Type of treatment” [Second-line treatment period / TREAT. TREAT_ty] = “EGFR-TKI” AND
 - “Start date of this line (dd/mmm/yyyy)” [Second-line treatment period / TREAT. TREAT_start_date] is lower than or equal to (“Date of data collection (dd/mmm/yyyy)” [PI. PI_date_coll] – 11.50 months) AND
 - “EGFR mutations at start of first-line treatment” [First-line treatment period / MUT1. MUT1_unc] OR “EGFR mutations at start of second-line treatment” in the MUTATIONS form of the [Second-line treatment period / MUT2. MUT2_mut_start] has at least one of the options selected (excluding “Del19” and “L858R”) (*)

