- For UNCOMMON MUTATION COHORT, it will be defined according to the fields **[First-line treatment period / MUT1. MUT1_unc, MUT1_unc_ex20_sp, MUT1_unc_sp]**.
- For SEQUENCING COHORT, it will be defined according to the field **[First-line treatment period / MUT1. MUT1_seq]**.

EGFR mutational status at second-line treatment start

It will be defined according to the following fields recorded in the MUTATIONS form of the [**Second-line treatment period**] time period (when applicable); for UNCOMMON MUTATION COHORT, only patients with Number of NSCLC treatment lines (as defined before) >1 should be considered:

- if “Was mutational status re-evaluated at start of second-line treatment?” [**MUT2. MUT2_reeval**] = “No” OR if “Any changes in EGFR mutations at start of second-line treatment with respect to start of first-line treatment?” [**MUT2. MUT2_changes**] = “UNK”, patients will be classified as “Unknown EGFR mutational status”
- if “Any changes in EGFR mutations at start of second-line treatment with respect to start of first-line treatment?” [**MUT2. MUT2_changes**] = “No”, then the patient’s EGFR mutational status at second-line treatment start will be imputed as the same patient’s EGFR mutational status at first-line treatment start (as defined before)
- if “Any changes in EGFR mutations at start of second-line treatment with respect to start of first-line treatment?” [**MUT2. MUT2_changes**] = “Yes”, then the patient’s EGFR mutational status at second-line treatment start will be retrieved from the fields [**MUT2. MUT2_mut_start**, **MUT2_mut_start_ex20_sp**, **MUT2_mut_start_sp**, **MUT2_concom_mut_start**]

Acquired EGFR mutations at second-line treatment start

For both cohorts, the mutations found at start of second-line treatment (i.e. the options selected in the field [**MUT2. MUT2_mut_start**]) will be compared to the mutations found at start of first-line treatment (i.e. the options selected in the field [**MUT1. MUT1_mut_unc**] for the UNCOMMON MUTATION COHORT, or in the field [**MUT1. MUT1_mut_seq**] for the SEQUENCING COHORT). The mutations found at start of second-line treatment that were not present at first-line treatment start will be classified as acquired EGFR mutations.

EGFR mutational status at second-line treatment stop/end of observation

It will be defined according to the following fields recorded in the MUTATIONS form of the [**Second-line treatment period**] time period (when applicable):

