- if “Was mutational status re-evaluated at at stop of second-line treatment (or within end of observation, in case second-line treatment was not discontinued)?” [**MUT2. MUT2_reeval_stop**] = “No” OR if “Any changes in EGFR mutations with respect to start of second-line treatment?” [**MUT2. MUT2_changes_stop**] = “UNK”, patients will be classified as “Unknown EGFR mutational status”
- if “Any changes in EGFR mutations with respect to start of second-line treatment?” [**MUT2. MUT2_changes_stop**] = “No”, then the patient’s EGFR mutational status at second-line treatment stop/end of observation will be imputed as the same patient’s EGFR mutational status at second-line treatment start (as defined before)
- if “Any changes in EGFR mutations with respect to start of second-line treatment?” [**MUT2. MUT2_changes_stop**] = “Yes”, then the patient’s EGFR mutational status at second-line treatment stop/end of observation will be retrieved from the fields [**MUT2. MUT2_mut_stop**, **MUT2_mut_stop_ex20_sp**, **MUT2_mut_stop_sp**, **MUT2_concom_mut_stop**]

Acquired EGFR mutations at second-line treatment stop/end of observation

For both cohorts, the mutations found at stop of second-line treatment/end of observation (i.e. the options selected in the field [**MUT2. MUT2_mut_stop**]) will be compared to the mutations found at start of second-line treatment (i.e. the options selected in the field [**MUT2. MUT2_mut_start**]). The mutations found at second-line treatment stop/end of observation that were not present at start of second-line treatment will be classified as acquired EGFR mutations.

Classification of EGFR uncommon mutations (according to Yang's classification) for exploratory analyses

According to the MUTATIONS form, considering the EGFR mutational status at first- and second-line treatment start (but considering only lines containing EGFR-TKIs), the following definitions will be applied to classify patients' mutational status with respect to EGFR gene:

- **T790M-positive:** patients having T790M at start of either first- or second-line EGFR-TKI, but excluding patients developing acquired T790M at second-line osimertinib start;
- **Exon 20 insertion-positive:** patients having any type of exon 20 insertion at start of either first- or second-line EGFR-TKI, excluding patients included in group "a");

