4.1.5 Time on treatment

Table 36-UNC. Time on treatment with index therapy EGFR-TKI (ELIGIBLE PATIENTS of the Uncommon Mutation Cohort) – Primary objective

The table will provide the Kaplan-Meier estimates of quartiles of time on treatment with index therapy EGFR-TKI (with their 95% Confidence Intervals, using Greenwood's variance estimate) (see "Computed variables" chapter).

Moreover, a Kaplan-Meier survival curve will be provided. The analysis will be represented on a plot having the time to event on the horizontal axis and the percentage of event-free patients on the vertical axis.

Table 37-UNC. Time to second-line treatment failure (ELIGIBLE PATIENTS of the Uncommon Mutation Cohort) – Secondary objective #4

The table will provide the Kaplan-Meier estimates of quartiles of time to second-line treatment failure (with their 95% Confidence Intervals, using Greenwood's variance estimate) (see "Computed variables" chapter).

Moreover, a Kaplan-Meier survival curve will be provided. The analysis will be represented on a plot having the time to event on the horizontal axis and the percentage of event-free patients on the vertical axis.

[figure not shown]
The analysis will be performed on ELIGIBLE PATIENTS in the cohort, considering only patients with Number of NSCLC treatment lines >1 (see "Computed variables" chapter) while excluding those with mutation T790M acquired only at second-line osimertinib start.

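### SAP criterion 10 looks for acquired T790M at the end of second-line osimertinib, so its data check cannot catch the patients protocol exclusion 3 removes

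*SAP*

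**What the plan says.** Protocol 9.2.1, exclusion 3, reads: "For uncommon mutation cohort: Patients treated with osimertinib with no further uncommon mutation than acquired T790M". Protocol 7.1 gives the reason: the evidence for osimertinib in acquired T790M is regarded as sufficient. The T790M in question is therefore already present when osimertinib starts.

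SAP 2.1, criterion 10, applies this exclusion in three ways: the investigator's answer on the eligibility form, the protocol deviation flag, and two checks on the recorded mutations, one per treatment line. The second-line osimertinib check marks a violation when three things hold together:

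- nothing beyond Del19/L858R is selected at first-line start (MUT1_unc);
- nothing beyond Del19/L858R is selected at second-line start (MUT2_mut_start);
- "AND only option “T790M” is selected in field “EGFR mutations” at stop of second-line treatment/within end of observation" (MUT2_mut_stop).

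Elsewhere the SAP places T790M acquired before osimertinib at second-line start:

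- Section 3, acquired mutations: "The mutations found at start of second-line treatment that were not present at first-line treatment start will be classified as acquired EGFR mutations".
- Section 3, T790M-positive class: "but excluding patients developing acquired T790M at second-line osimertinib start".
- Section 4.1.5, Table 37-UNC: "while excluding those with mutation T790M acquired only at second-line osimertinib start".
- Section 2.1, criterion 6 of the sequencing cohort, reads T790M from MUT2_mut_start.

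Criterion 5 of the uncommon cohort asks only this of the mutation data: "At least one uncommon mutation shall be present on the start date of the Index EGFR-TKI therapy". The index-therapy rule in section 3 accepts any option other than Del19 or L858R, so T790M alone qualifies.

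**The concern.** The check reads T790M one time point too late. A patient with Del19 at first line who acquires T790M and then starts osimertinib has T790M in MUT2_mut_start. That makes the second condition false, and the check stays silent on exactly the patient that exclusion 3 describes. T790M that is absent at second-line start and present at stop appeared after osimertinib began, which is a different situation.

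The ELIGIBLE set feeds the primary analysis of time on treatment (Table 36-UNC) and overall survival (Table 38-UNC). The visible text of those two tables carries no T790M restriction of its own. The planned quality control may not reveal the error either: section 6 has the Table 2-UNC algorithms checked for every enrolled patient, but that compares the program with the SAP rule, and here the rule is at fault.

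**Working it through.** The documents give no figure to reproduce; this is a test of eligibility logic.

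**Inputs.** Second line is osimertinib and the start-date conditions are taken as met. MUT1_unc takes one of 5 states, apart from Del19/L858R: none, T790M, other uncommon, both, untested. MUT2_mut_start takes one of 4 states: none, T790M, other, both. This gives 5 × 4 = 20 patterns. Each was run over 4 stop states, with and without a Del19/L858R tick at second-line start, and with chemotherapy, another EGFR-TKI or osimertinib as first line. The results below for the second-line check and criterion 5 are the same across these variations, apart from the stop state needed for the check to fire.

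**Rules.**

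- Criterion 5 (mutation part) is met if there is any uncommon option at first- or second-line start.
- The check as written fires if MUT1_unc has no uncommon option, MUT2_mut_start has none, and MUT2_mut_stop is T790M only.
- The target of exclusion 3 is first line tested with no uncommon mutation, and T790M the only uncommon option at second-line start.

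| Pattern (first-line start, second-line start) | Criterion 5 | Check as written | Corrected check |
|---|---|---|---|
| none, none | fails | fires if stop is T790M only | silent |
| untested, none | fails | fires if stop is T790M only | silent |
| none, T790M (target) | met, index is second-line osimertinib | never fires | violation |
| untested, T790M | met | never fires | query |
| other 16 patterns | met | never fires | silent |

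**Counts.** Criterion 5 is met in 20 − 2 = 18 patterns. The check as written can fire in 2, and 0 of these 2 meet criterion 5, so it removes nobody whom criterion 5 would keep. It catches the target 0 times. With the corrected check, 18 − 1 = 17 patterns meet criterion 5 and are not excluded; 1 of the 17 goes to query.

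**Second enumeration.** Using Del19, G719X and T790M as representative mutations, each time point has 2³ = 8 mutation sets. With 2 first-line types there are 2 × 8 × 8 × 8 = 1,024 profiles.

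- Target profiles: 2 × 2 × 2 × 8 = 64. Caught as written: 0. All 64 have second-line osimertinib as index therapy.
- Profiles flagged as written, reading the stop condition as T790M being the only uncommon option: 2 × 2 × 2 × 2 = 16. None has an index EGFR-TKI.
- Corrected check: 64 of 64 caught. This holds by construction.

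The informative result for the correction is the untested row: without a query, T790M of unknown origin would be treated as acquired.

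**The case against.** The strongest reply is that exclusion 3 is still applied. Criterion 10 requires a negative answer on the eligibility form and no protocol deviation flag, both in the protocol's own terms. The data check only backs these up. SAP criteria 8 and 9, which carry the other two exclusions, rest on the same two forms alone. A target patient reaches the primary table only if the investigator answers an explicit question wrongly and nobody flags a deviation, and Protocol 9.8 plans source verification on about 30% of patients. This limits the consequence, and it stands. It does not repair the check: the SAP chose to include one, and it tests the wrong time point.

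Three further points have some force.

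- The wording in Table 37-UNC and in the T790M-positive class can also cover patients with another uncommon mutation at first line. It establishes when the SAP records acquired T790M, not that target patients are in the data.
- If osimertinib is given in both lines and neither Del19 nor L858R is ticked at second-line start, the first-line check, read literally, fires on the target pattern. One narrow data-driven route therefore survives. The first-line check is otherwise outside this point.
- An untested first line also shows no uncommon option, so a corrected rule could declare a violation and raise a query at once. The fix must say which comes first. If the query did not take precedence, 16 patterns would remain, not 17.

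**Conclusion.** The concern holds. The second-line osimertinib check in criterion 10 is false for every patient that exclusion 3 targets, and it is redundant with criterion 5 for every patient it can flag. No other SAP passage repairs it.

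The pattern counts describe logic, not patients. The documents do not allow the number affected to be derived, and it may be zero. For scale, each such patient left in would be 1/250 = 0.4% of the planned uncommon cohort. The conclusion assumes that T790M acquired before osimertinib is entered at second-line start, as SAP section 3 provides, and that the start-date conditions are met. It should be corrected because it is a stated eligibility rule feeding the primary analysis; the working form checks keep it from being more serious.

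**What to change.** Replace the second-line osimertinib bullet of criterion 10 with this rule: if second line is osimertinib, criterion 10 is violated when MUT1_unc has no option other than Del19/L858R and T790M is the only option in MUT2_mut_start, disregarding Del19/L858R. Delete the MUT2_mut_stop condition.

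Add a query for any patient whose EGFR status at first-line start is missing or untested, and state that the query takes precedence: the data check does not count the patient as a violator unless the reply confirms testing with no uncommon mutation. A Del19 or L858R tick shows that the patient was tested; a blank field does not.

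Leave the index EGFR-TKI definition unchanged. A violation found only by the data check then falls under item 18 of the hierarchy in SAP 2.5.1. If the index definition were also altered, these patients would have no index therapy, would fail criteria 2 and 5, and would be reported under items 4 or 8, which hides the true reason.

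The cost is one SAP wording change, one reprogrammed check on fields the SAP already names, and one query rule. No new eCRF field should be needed. The eCRF itself is not among the documents, so confirm how an untested first line is recorded.
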